9.2.3 Study Cohorts

The study will include four primary cohorts identified from all eligible individuals in the study population who are prescribed topical tacrolimus, topical pimecrolimus, or moderate- to high-potency topical corticosteroids during the study period, and one secondary cohort of untreated patients (Figure 2).

Figure 2. Selection of Study Cohorts

The primary study cohorts are defined as follows:

- *Tacrolimus-exposed cohort (tacrolimus cohort)*: patients receiving a first prescription for topical tacrolimus during the study period after the eligibility date
- *Pimecrolimus-exposed cohort (pimecrolimus cohort)*: patients receiving a first prescription for topical pimecrolimus during the study period after the eligibility date
- *Two cohorts of users of moderate- to high-potency topical corticosteroids (corticosteroids cohorts)*. Two comparative cohorts, one for the tacrolimus cohort and one for the pimecrolimus cohort will be identified from all eligible individuals from the study population meeting *one* of the following criteria:
 - Individuals with a recorded diagnosis of atopic dermatitis at any time before the start date who received a prescription for moderate- to high-potency corticosteroids during the study period after the eligibility date.
 - Individuals without a recorded diagnosis of atopic dermatitis before the start date who received a prescription for moderate- to high-potency corticosteroids during the study period after the eligibility date and at least one other prescription (for moderate- to high-potency topical corticosteroids) within the 12 months before the start date.

To identify the two corticosteroids cohorts, propensity scores will be estimated separately for the tacrolimus cohort and the pimecrolimus cohort. Users of corticosteroids will be frequency matched to users of tacrolimus and pimecrolimus according to categories of percentiles of propensity scores estimated for each exposed cohort.

The study will include a secondary cohort to address the secondary study objective of comparing users of moderate- to high-potency corticosteroids versus the untreated

population, attempting to put in population perspective the magnitude of any changes in risk observed between the study cohorts:

- *Untreated cohort.* A comparative cohort of patients not receiving treatment with any of the study medications will be identified among all eligible individuals from the study population. The untreated cohort will be matched to the corticosteroids cohort that was identified as the comparative cohort for users of tacrolimus. Individual matching will be conducted on year of birth, sex, primary care general practice/region, and calendar year of start date.

Each of these study cohorts is described in more detail below.

9.2.3.1 Tacrolimus Cohort and Pimecrolimus Cohort

[figure not shown]
Patients will be included in the tacrolimus cohort or the pimecrolimus cohort according to the first medication prescribed during the study period. If the first prescription a patient receives is for topical tacrolimus, that patient will be included in the tacrolimus cohort. The date of that first prescription is defined as the start date, the date of cohort entry. Once a patient enters one of the exposed cohorts (tacrolimus cohort or pimecrolimus cohort) that patient remains in that cohort until the end of follow-up. Therefore, patients entering the tacrolimus cohort or the pimecrolimus cohort cannot contribute person-time to the other study cohorts after becoming exposed (see Section 9.3.4, Exposure Assessment, for further details on the classification of person-time).

The indication for topical tacrolimus and topical pimecrolimus is restricted to the treatment of atopic dermatitis. However, these medications might be used to treat other skin conditions such as psoriasis or other inflammatory skin diseases. For the purpose of this study, we assume that all patients included in the tacrolimus cohort and the pimecrolimus cohort have atopic dermatitis whether or not a diagnosis of atopic dermatitis is recorded in the study databases. To characterize users of tacrolimus and pimecrolimus, we will ascertain at the start date diagnosis of atopic dermatitis, diagnosis of other skin conditions, and prior treatments (e.g., topical corticosteroids).

9.2.3.2 Corticosteroids Cohorts

Topical corticosteroids have multiple indications of use. The two corticosteroids cohorts will be identified in each database from (1) all eligible individuals from the study population who have a diagnosis of atopic dermatitis at any time before the start date and received a prescription for moderate- to high-potency corticosteroids and (2) all eligible individuals without a diagnosis of atopic dermatitis any time before the start date who received a prescription for moderate- to high-potency corticosteroids during the study period and at least one other prescription within the prior 12 months (Figure 3). (See Section 9.3.1, Identification of Atopic Dermatitis, for further details on the atopic dermatitis criteria.)

Figure 3. Users of Moderate- to High-Potency Corticosteroids With Two Prescriptions Within a Period of 12 Months

Individuals meeting these criteria will be used to estimate propensity scores separately for the tacrolimus cohort and the pimecrolimus cohort. A person can be included in both corticosteroids cohorts, the comparative cohort for tacrolimus and the comparative cohort for pimecrolimus. The propensity score represents the predicted probability of receiving each corresponding treatment instead of receiving moderate- to high-potency topical corticosteroids. The percentiles of propensity scores estimated for each exposed cohort will be classified in 20 strata (twentiles). Users of corticosteroids will be frequency matched to users of tacrolimus and pimecrolimus according to the strata of propensity scores of each exposed cohort. A matching ratio (corticosteroids to tacrolimus or pimecrolimus) up to 4:1, depending on available matches, will be used across strata. The strata of propensity scores will be used to conduct an overall stratified analysis combining the data from the study databases. Separate propensity scores and strata of propensity scores will be calculated for the pediatric and adult populations.

Patients in the two corticosteroids cohorts should meet the criteria either for atopic dermatitis or for the number of corticosteroids prescriptions at the time of receiving the first prescription for moderate- to high-potency corticosteroids (Figure 3) (see Section 9.3.1, Identification of Atopic Dermatitis, for further details). The date of the first prescription during the study period for moderate- to high-potency corticosteroids is defined as the start date. Patients in the corticosteroids cohorts can be prevalent or new users of moderate- to high-potency corticosteroids. Patients in the corticosteroids cohorts can contribute person-time to the tacrolimus cohort or the pimecrolimus cohort during follow-up should they receive a prescription for tacrolimus or pimecrolimus. In that situation, patients will be censored from the corticosteroids cohort at the date of receiving a prescription for tacrolimus or pimecrolimus.

9.2.3.3 Untreated Cohort

The untreated cohort will be identified from all eligible patients from the study population and will be used as the reference in the comparison with the corticosteroids cohort identified for users of tacrolimus (Figure 2). Individuals in the untreated cohort are not

required to have a diagnosis of atopic dermatitis. The untreated cohort will be individually matched to the corticosteroids cohort on year of birth, sex, primary care general practice/region, and calendar year of start date, with a matching ratio up to 4:1. The selected match in the untreated cohort must be eligible on the start date of the matched corticosteroids cohort member; the untreated cohort member will be assigned the start date of the matched corticosteroids cohort member.

Patients in the untreated cohort can contribute person-time to any of the other four study cohorts during follow-up and will be censored from the untreated cohort at the date of receiving a prescription for tacrolimus, pimecrolimus, or a moderate- to high-potency corticosteroid.

In Phase I, we evaluated the feasibility of conducting a sensitivity analysis to include an untreated cohort with atopic dermatitis. The identification of individuals with atopic dermatitis not treated with the study medications is difficult because most of these patients would have been treated with topical medications at some point during the natural course of their disease. Because we are studying a long-term effect (malignancy), we do not know the impact that early treatments could have on the study endpoint. In addition, early treatments might not be captured in the study databases. For example, the prescription register in Sweden is quite recent and includes medications dispensed only since 2005. Another limitation is that untreated patients might include those who are at the initial stage of the disease when a diagnosis of atopic dermatitis might not yet have been confirmed. Some of these patients might be diagnosed with atopic dermatitis at a later time, but others might be diagnosed with other skin disease or with an acute or transitory skin condition. Therefore, a potential untreated cohort might include patients with heterogeneous skin conditions.

Results from Phase I showed that the prevalence of recorded atopic dermatitis in the study databases, except the CPRD, was very low. Therefore, the sensitivity analysis restricted to patients with atopic dermatitis was not conducted. This analysis will also not be conducted in the JOELLE Extension.

9.2.4 Follow-up

Follow-up after entry into each cohort (start date) will continue until the earliest of occurrence of one of the following: first occurrence of any one of the study endpoints, death, disenrollment from the study databases, or end of the study period.

In a sensitivity analysis, patients will be followed for the occurrence of each specific endpoint regardless of a prior occurrence of any of the other study endpoints during the study period.

9.3 Variables

9.3.1 Identification of Atopic Dermatitis

Ascertainment of atopic dermatitis based on recorded diagnoses will be performed in a first step for the identification of members of the corticosteroids cohorts across databases.

PHARMO, Denmark, and Sweden

In the databases of PHARMO, Denmark, and Sweden, hospital inpatient and/or outpatient ICD-10 diagnoses are available for the full cohorts of users of corticosteroids.

In Phase I, the application of an algorithm, originally planned to predict atopic dermatitis status (yes/no) in the corticosteroids cohorts, was discarded due to the low positive predictive value found in the prediction models. Subsequently, application of clinical algorithm criteria to ascertain atopic dermatitis was considered based on (1) individuals with a primary or secondary hospital outpatient or inpatient discharge diagnosis of atopic dermatitis at any time before the start date or (2) individuals with at least two prescriptions for moderate- to high-potency topical corticosteroids within a period of 12 months AND who do not have any prescription for specific exclusion medications (e.g., topical or systemic antipsoriatic drugs, topical salicylic acid preparations) or any hospital discharge or outpatient diagnosis for a specific disease (e.g., psoriasis and similar disorders, vitiligo, scleroderma) within 12 months prior to the start date. These exclusion criteria were also applied to the tacrolimus and pimecrolimus cohorts to achieve comparable cohorts. An exploratory analysis was performed in the databases of Sweden and PHARMO to assess the impact that the exclusion of specific medications or diagnoses would have in the tacrolimus and pimecrolimus cohorts. The results showed that approximately 50% of the members of the tacrolimus and pimecrolimus cohorts would be excluded. Such a substantial reduction in these study cohorts was considered not acceptable. Therefore, these exclusion criteria will not be applied to the corticosteroids cohorts or to the tacrolimus and pimecrolimus cohorts. The corticosteroids cohorts will be defined as (1) individuals with a recorded diagnosis of atopic dermatitis who are users of moderate- to high-potency corticosteroids during the study period and (2) individuals without a recorded diagnosis of atopic dermatitis who received at least two prescriptions of moderate- to high-potency topical corticosteroids within a period of 12 months. This definition of the corticosteroids cohorts improves their comparability with the tacrolimus and pimecrolimus cohorts as the inclusion criteria are expanded to include patients without a recorded diagnosis of atopic dermatitis, so they are similar to the inclusion criteria for the tacrolimus and pimecrolimus cohorts.

It should be noted that the absence of a recorded diagnosis of atopic dermatitis in the study databases does not indicate by itself off-label use of tacrolimus or pimecrolimus. The extent to which diagnoses are recorded depends on the type of database, whether it is based on primary care or hospital diagnoses, compliance of physicians with local recording requirements, type of diagnoses, and other parameters. The indication of medications is usually not recorded in most databases. In some primary care databases (e.g., the CPRD) physicians are encouraged to record the indication of new medications. Evaluation of the indication and off-label prescribing of medications usually requires the clinical review and assessment of diagnoses, free text, and medical records when these are available.

CPRD

In the CPRD, patients with atopic dermatitis within the corticosteroids cohorts will be identified using Read codes, the standard clinical terminology system used in general practice in the UK. In Phase I, the diagnosis of atopic dermatitis was validated in a random sample of 60 children and 40 adult patients by reviewing free-text comments and the computerized medical history. The positive predictive value of using Read codes to identify these patients was 95.0% in children and 87.5% in adults.

9.3.2 Study Medications

The study medications of interest are topical tacrolimus, topical pimecrolimus, and topical corticosteroids. The Anatomical Therapeutic Chemical (ATC) classification for topical tacrolimus and topical pimecrolimus is as follows:

- Tacrolimus (D11AH01); available as 0.03% and 0.1% ointment
- Pimecrolimus (D11AH02); available as 1% cream

Topical corticosteroids will be classified according to their potency. The ATC classification for topical corticosteroids is as follows:

- Topical corticosteroids, plain
 - Weak (D07AA)
 - Moderately potent (D07AB)
 - Potent (D07AC)
 - Very potent (D07AD)
- Topical corticosteroids, combinations with other agents
 - Weak (D07BA, D07CA, D07XA)
 - Moderately potent (D07BB, D07CB, D07XB)
 - Potent (D07BC, D07CC, D07XC)
 - Very potent (D07BD, D07CD, D07XD)

Corticosteroids with an ATC classification of moderately potent, potent, or very potent are the corticosteroids of interest to this study and will be classified together as moderate- to high-potency corticosteroids.

Children with atopic dermatitis may be prescribed moderate- to high-potency corticosteroids infrequently, which may impact the inclusion of pediatric patients using these medications.

9.3.3 New Users

A new user of topical tacrolimus or topical pimecrolimus is defined as any user that has not been prescribed either topical tacrolimus or topical pimecrolimus at any time before the date of cohort entry. New users can be identified in the four study data sources, although some degree of misclassification of prevalent users as new users is possible in the CPRD and Sweden. In the CPRD, prescriptions initiated by a specialist (e.g., dermatologist) may not be recorded in the database. Although subsequent prescriptions are managed by the GP, some patients might be prevalent users at the time of the first recorded prescription in the CPRD and be misclassified as new users. Because the prescription register in Sweden is available only since July 2005, in this data source, new users are defined as those patients who did not fill any prescription for topical tacrolimus or topical pimecrolimus between July 1, 2005, and July 1, 2016. Users of topical tacrolimus or pimecrolimus entering the study cohort might be past users of these medications because topical tacrolimus was approved in 2002 and topical pimecrolimus in 2003. The eligibility criterion of 12 months of continuous enrollment will result in the exclusion of patients receiving a prescription for the study medications during that period.

9.3.4 Exposure Assessment

To assess the effect of exposure to topical tacrolimus and topical pimecrolimus, we assume that exposure to either of the two medications results in a lifetime change in risk for the effects of that specific medication. That is, if a patient is exposed to topical tacrolimus (tacrolimus cohort), the status of exposure to tacrolimus is maintained throughout follow-up even after stopping therapy with tacrolimus. However, time at risk will start after the lag time of 6 months is completed.

Accordingly, person-time of follow-up of each cohort (topical tacrolimus and topical pimecrolimus) will be classified in several categories of exposure.

[figure not shown]
9.3.4.1 Exposure to Topical Tacrolimus

- *Ever use of topical tacrolimus:* person-time starting 6 months after the date of the first prescription for topical tacrolimus to the end of follow-up (Figure 4). In this exposure category, any potential switching to topical pimecrolimus is ignored (all person-time of follow-up is allocated to topical tacrolimus).

In addition, the overall person-time of follow-up of topical tacrolimus will be classified in two mutually exclusive categories (Figure 4):

- *Single use of topical tacrolimus (monotherapy with topical tacrolimus):* person-time starting 6 months after the date of the first prescription for topical tacrolimus to the earliest of the following dates: 6 months after the date of receiving a prescription for topical pimecrolimus or date of end of follow-up.
- *Switching (from topical tacrolimus to topical pimecrolimus)/multiple use:* person-time starting 6 months after the date of receiving a prescription for topical pimecrolimus to the end of follow-up.

Figure 4. Exposure Assessment: Example for Exposure to Topical Tacrolimus

9.3.4.2 Exposure to Topical Pimecrolimus

The same exposure rationale described for topical tacrolimus will be implemented for defining exposure to topical pimecrolimus, with pimecrolimus as the first exposure and tacrolimus as the second or additional exposure.

9.3.4.3 Exposure to Both Topical Tacrolimus and Topical Pimecrolimus

- *Combined multiple use:* in addition, person-time starting 6 months after switching between the two study drugs will be combined in a single overall category of switching/multiple use to assess the effect of the overall exposure to both drugs after switching.

9.3.4.4 Cumulative Exposure

Cumulative exposure will be used as the main measure of exposure in the analysis and will be calculated as the cumulative dose of tacrolimus or pimecrolimus a patient receives during follow-up. Dose will be accumulated daily according to the milligrams prescribed and the estimated average duration of prescriptions. The milligrams prescribed will be calculated according to the strength of the formulation and the package size. The average duration of prescriptions will be estimated separately for children and adults from preliminary descriptive analysis of the time between consecutive prescriptions. The average duration of prescriptions used in Phase I will be used in the JOELLE Extension.

Cumulative exposure will be categorized in levels of exposure (e.g., low, medium, and high) according to the distribution of cumulative exposure in the study databases. The number of levels of cumulative exposure and cut-off values will be decided after examining the distribution of cumulative exposure across databases. Patients will contribute time of follow-up to each level of cumulative exposure according to the cumulative dose received. For each level of cumulative exposure, we will assume an induction period of 6 months for the start of exposure effects. Thus, the time at risk will start 6 months after reaching the cut-off value of each cumulative exposure category. Cumulative exposure will be assessed for tacrolimus and for pimecrolimus for each of the exposure categories described in Section 9.3.4.1 (ever use, single use, and switching/multiple use) and for combined multiple use of both tacrolimus and pimecrolimus (Section 9.3.4.3).

[figure not shown]
9.3.4.5 Duration of Exposure

Duration of exposure will be calculated as the total time of use of topical tacrolimus or pimecrolimus. A maximum time interval between prescriptions will be estimated from preliminary descriptive analysis to define consecutive prescriptions. Duration of exposure will be categorized after examining the duration distribution of each database.

9.3.4.6 Cohort of Users of Corticosteroids

Person-time will be accumulated from the date of cohort entry to the earliest of the following dates: prescription for topical tacrolimus, prescription for topical pimecrolimus, or end of follow-up (Figure 5).

[figure not shown]
Figure 5. Exposure Assessment: Example for Patients Contributing Person-time to Both the Corticosteroids Cohort and the Tacrolimus Cohort

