When estimating incidence rates we will assume a minimum lag time of 6 months between the start of treatment and the occurrence of the study endpoints. This implies that person-time for the interval of the first 6 months since start of treatment will be excluded, along with any events that occur within this time period. This lag time encompasses a period of drug utilization and dose accumulation, a period of induction time (from causal action of exposure to disease initiation), and a latency period (from disease initiation to disease detection). The induction time for the occurrence of skin cancer and lymphomas associated with the use of tacrolimus and pimecrolimus is unknown. Therefore, we will conduct sensitivity analyses to estimate incidence rates within the first 6 months of treatment and for several lag times longer than the initial 6 months. The lag time analysis will also be used to explore potential protopathic bias if early symptoms of skin cancer or lymphoma are erroneously treated as atopic dermatitis and therefore the reason for starting treatment.

The goal of the first secondary objective is to obtain background rates among persons not treated with the study medications and to put in perspective potential differences among the untreated population, the atopic dermatitis cohort treated with moderate- to high-potency corticosteroids (see Section 9.3.1, Identification of Atopic Dermatitis, for further details on atopic dermatitis criteria), and the tacrolimus cohort.

9 Research Methods

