9.3.4.7 Untreated Cohort

Person-time will be accumulated from the start date (see Section 9.2.3.3) to the earliest of the following dates: prescription for moderate- to high-potency topical corticosteroids, prescription for topical tacrolimus, prescription for topical pimecrolimus, or end of follow-up (Figure 6).

Figure 6. Exposure Assessment: Example for Patients Contributing Person-time to the Untreated Cohort and Any Other Cohort

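### The 6-month lag is written for tacrolimus and pimecrolimus but not for the corticosteroid comparator, which conflicts with Section 8 and can bias the primary rate ratios downward

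*Protocol*

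**What the plan says.** Section 8 gives the general rule for estimating incidence rates: "person-time for the interval of the first 6 months since start of treatment will be excluded, along with any events" in that interval. It names no cohort. It adds that the lag analysis will serve to explore protopathic bias, meaning treatment started because of early symptoms of the cancer.

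The exposure sections make the rule specific.

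- **Both calcineurin inhibitors (9.3.4).** "However, time at risk will start after the lag time of 6 months is completed".
- **Tacrolimus, ever use (9.3.4.1).** "person-time starting 6 months after the date of the first prescription for topical tacrolimus to the end of follow-up".
- **Pimecrolimus (9.3.4.2).** "The same exposure rationale described for topical tacrolimus will be implemented for defining exposure to topical pimecrolimus".
- **Corticosteroids (9.3.4.6).** "Person-time will be accumulated from the date of cohort entry to the earliest of the following dates: prescription for topical tacrolimus", or the first pimecrolimus prescription, or end of follow-up. Cohort entry is the start date, that is, the date of the qualifying corticosteroid prescription (Key Definitions).
- **Untreated (9.3.4.7).** "Person-time will be accumulated from the start date" of the matched corticosteroid user.

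Section 9.7.2.3 makes the corticosteroid cohort the reference for the primary IRRs. Sensitivity analysis 7 in 9.7.2.5 estimates rates and IRRs for the first 6 months and for other lags, with examples from 12 to 48 months. It is framed for single use of tacrolimus and pimecrolimus and does not say what happens to the comparator's clock.

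**The concern.** A lag meant to remove cancers already present when treatment began should act on both sides of a rate ratio. The protocol itself regards corticosteroid users as open to the same bias. Section 7.1 says undiagnosed cutaneous T-cell lymphoma (CTCL) may be treated as atopic dermatitis. Section 9.3.6.1 asks general practitioners why corticosteroids were prescribed, and 9.7.2.6 examines reverse causation in corticosteroid users, though only against untreated patients.

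If the comparator is not lagged, its early events raise the reference rate while the matching events are removed from the exposed side. Section 9.9 bases interpretation on the point estimate, the upper confidence limit and the absolute excess risk. A downward bias would therefore make the study look more reassuring than it should. Four database partners adapt and program this core protocol, and 9.3.4.6 is the specific rule they will find for the comparator.

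**Working it through.** **1. Text comparison.** If Section 8 covers corticosteroids, 9.3.4.6 contradicts it. If it does not, the two sides of the primary IRR use different clocks. No other section lags the comparator, so the sections need reconciling on either reading.

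**2. Share of person-time in the first 6 months, f.** The protocol gives no follow-up distribution for corticosteroid users, so I assume it resembles that of adult tacrolimus users in the Extension.

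- *Check on the plan's own figure.* Table 6 has 103,175 users. Interval midpoints give 602,954 person-years. Removing half a year per user (103,175 × 0.5 = 51,588) leaves 551,366, against 551,369 in Table 3. Table 3 is thus after the lag and Table 6 before it.
- *From Table 6.* Users still followed at 6 months, by interpolation: (103,175 + 102,143)/2 = 102,659. Person-years in months 0 to 6: 0.5 × (103,175 + 102,659)/2 = 51,459. Share: 51,459/602,954 = 8.5%.
- *From Table 3.* Mean follow-up after the lag is 551,369/98,788 = 5.58 years, so f = 0.5/(5.58 + 0.5) = 8.2%.

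**3. Effect on the IRR.** Let k be the comparator's event rate in months 0 to 6 divided by its later rate. The documents do not give k; it is an assumption. The reference rate is inflated by 1 + f(k − 1), and observed IRR = true IRR / [1 + f(k − 1)].

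| k (assumed) | Inflation, f = 8.2% | True 1.0 reads as | True 1.5 reads as | True 1.5, f = 8.5% |
|---|---|---|---|---|
| 1 | 1.00 | 1.00 | 1.50 | 1.50 |
| 2 | 1.08 | 0.92 | 1.39 | 1.38 |
| 3 | 1.16 | 0.86 | 1.29 | 1.28 |

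If comparator follow-up were shorter, f would be larger. With the Phase I mean of 198,400/66,127 = 3.0 years taken as time after the lag, f = 0.5/3.5 = 14.3%, and a true 1.5 reads as 1.31 (k = 2) or 1.17 (k = 3).

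**4. In events: adult CTCL at the full 4:1 ratio.** Table 4 gives 3.1 per 100,000 person-years. Comparator events after the lag: 4 × 551,369 × 3.1/100,000 = 68.4. Early person-years: 4 × 98,788 × 0.5 = 197,576. Early events: 6.1 at k = 1, 12.2 at k = 2, 18.4 at k = 3.

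**5. With one lag on both sides,** the early events leave both rates, and a true IRR of 1.0 is estimated as 1.0 whatever k is.

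**The case against.** Section 8 and the abstract state the lag in terms that fit all cohorts, and 9.7 leaves the calculation of person-years to the statistical analysis plan. Figure 5, which I could not see, may show a lag for corticosteroid users. The intention may well be symmetric. That stands as a reason to call this a conflict to reconcile rather than a settled one-sided design. It does not remove the conflict, because 9.3.4.6 fixes a starting point.

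Four stronger readings are tempting but not supported.

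- **That every primary IRR is biased downward.** The bias needs an early excess in the comparator, and the protocol quantifies none for any endpoint. Corticosteroid users may be prevalent users (9.2.3.2). Those without a recorded diagnosis of atopic dermatitis must have had another prescription in the prior 12 months. For them, the first 6 months after entry are not the first 6 months of treatment, which may dilute any excess.
- **That the relative risks in Section 7.1 demonstrate an early excess.** The published values for corticosteroids (3.8, 14.8, 25.8, 12.9 and 82.9) are by duration of use, concern lymphomas with skin involvement, and do not fall steadily after 6 months. They suggest that corticosteroid users are open to the bias but say nothing about k.
- **That the exit rule should change too.** Tacrolimus single use runs until "6 months after the date of receiving a prescription for topical pimecrolimus or date of end of follow-up", whereas 9.2.3.2 explicitly censors corticosteroid users at the switch. Extending their time by 6 months would add cancers that prompted the switch to the reference only, while the lag removes the same events from the exposed cohort. That would create the bias at issue here.
- **That the untreated comparison is asymmetric.** As written, both of its cohorts start at the start date.

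Sensitivity analysis 7 offers partial protection, since its first-6-months result could show an early difference. If its longer lags move only the exposed cohort, however, they widen the mismatch.

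**Conclusion.** The point holds as a conflict between Section 8 and 9.3.4.6. Followed literally, 9.3.4.6 gives the two sides of the primary IRRs different starting points. The direction is downward if corticosteroid users have an early protopathic excess. The size is unknown, and it is zero if there is no excess. The illustration of a true 1.5 read as about 1.4 to 1.3 rests on two assumptions: comparator follow-up like that of adult tacrolimus users, and a two- to three-fold early excess. It should not be read as an estimate of the bias in this study.

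**What to change.** 1. In 9.3.4.6, state that corticosteroid person-time and events at risk begin 6 months after the start date, and word Section 8 to match. Naming the start date matters because, for prevalent users, start of treatment is a different date.
2. In sensitivity analysis 7 of 9.7.2.5, state that the first-6-months analysis and each alternative lag apply to both cohorts.
3. In 9.3.4.7, apply the same lag to untreated patients, so that the secondary comparison stays symmetric once corticosteroid users are lagged.
4. Keep the censoring of corticosteroid users at the first tacrolimus or pimecrolimus prescription (9.2.3.2).

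No new data are needed. The comparator loses about 8% of its person-time. The loss of precision is small. For adult CTCL at 4:1 with k = 1 and 551,369 × 3.1/100,000 = 17.1 exposed events, the standard error of the log IRR goes from √(1/17.1 + 1/74.5) = 0.268 to √(1/17.1 + 1/68.4) = 0.270. The change should be made before the database partners run their core analyses.
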